
6.3 Assignment to Study Intervention
 
Other sections impacted are
 
Definition of Terms
 
1.1 Synopsis
 
1.2. Schema
 
1.3. Schedule of Activities
 
4. Study Design
	
The study design was modified as follows:
 
The requirement to stop efgartigimod PH20 SC when participants are in CR or PR while off concurrent BP therapy for ≥ 8 weeks was removed. Guidance was added for initiating efgartigimod PH20 SC without concurrent OCS and tapering or discontinuing rescue therapy started in ARGX-113-2009.
 
IMP will be permanently discontinued if the investigator considers it not to be in the participant’s best interest to taper or discontinue rescue therapy, or initiate efgartigimod PH20 SC.
	
To gain better insight into the safety and efficacy of efgartigimod PH20 SC without concurrent OCS or other BP therapy, and allow evaluation of whether maintenance therapy with efgartigimod PH20 SC can prevent relapse

3. Objectives, Endpoints, and Estimands
 
Other sections impacted are
 
1.1 Synopsis
	
The following footnote was added to the endpoints “Proportion of participants achieving CR while off both OCS and efgartigimod PH20 SC for ≥ 8 weeks” and “Proportion of participants achieving CR or PR while off both OCS and efgartigimod PH20 SC for ≥ 8 weeks”:
 
The endpoint applies only to participants who have stopped receiving efgartigimod PH20 SC before protocol amendment 2 is effective.
	
To align with updated design

6.1. Investigational Medicinal Product Administered
	
The following changes were made in the “intervention description” and “dosage level(s)” rows of Table 5:
 
At the start of a treatment course: 0.2 to 0.5 mg/kg/day
 
Thereafter: Initiated and adjusted according to clinical judgment
	
Concurrent OCS therapy is no longer required to be started at the same time as efgartigimod PH20 SC initiation

Section	Change in study conduct or planned analysis	Brief rationale
	
At the start of a treatment course: 0.2 to 0.5 mg/kg/day
 
Thereafter: adjusted according to clinical judgment
	

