In ARGX-113-2009, participants received efgartigimod PH20 SC or placebo with concurrent OCS, or rescue therapy (without efgartigimod PH20 SC or placebo). When rolling over to ARGX-113-2010, participants will either initiate or continue efgartigimod PH20 SC treatment, while maintaining the blinded treatment allocation of ARGX-113-2009 (refer to Section 6.4).

Before protocol amendment 2, participants had to stop receiving efgartigimod PH20 SC upon achieving CR or PR while off concurrent BP therapy for ≥ 8 weeks. After protocol amendment 2, participants who stopped efgartigimod PH20 SC will reinstate treatment at the investigator's discretion. If they relapse, reinstatement of efgartigimod PH20 SC treatment is mandatory. All other participants (ongoing and newly enrolled) will continue to receive efgartigimod PH20 SC until the end of the treatment period. Concurrent BP therapies, including rescue therapies started during ARGX-113-2009, will be tapered or discontinued. IMP will be permanently discontinued if the investigator considers it not to be in the participant's best interest to taper or discontinue rescue therapy or initiate efgartigimod PH20 SC.

Brief Summary: The purpose of this study is to evaluate the safety of efgartigimod PH20 SC over a longer period of time in adult participants with moderate-to-severe BP. The study will also evaluate the efficacy of efgartigimod PH20 SC.

Health Measurement/Outcome: The primary outcome measure is the long-term safety and tolerability of open-label efgartigimod PH20 SC for approximately 1 year after completing ARGX-113-2009.

Investigational Medicinal Product and Investigational Medicinal Product Formulation:

Efgartigimod PH20 SC [REDACTED]

Condition/Disease: Bullous pemphigoid

Study Duration: Approximately 56 weeks

Treatment Duration: Up to 48 weeks

Visit Frequency: Participants will visit the site at weeks 0 (baseline), 1, 2, 4, and 8. After that, participants will visit every 4 weeks. Participants not receiving efgartigimod PH20 SC will visit every 8 weeks. A treatment-free period of 8 weeks follows the EoTP visit at week 48, with visits at EoTP + 4 weeks (if receiving efgartigimod PH20 SC) and EoTP + 8 weeks.

Number of Participants: All participants who complete the EoTP visit (week 36) in ARGX-113-2009 and meet the eligibility criteria can roll over to this study. All participants rolling over agree to participate in the clinical study by completing the informed consent process.

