2. INTRODUCTION

ARGX-113-2010 intends to demonstrate that efgartigimod PH20 SC is a safe and effective long-term treatment for BP, providing symptom control and eventually remission, while also reducing the cumulative exposure to OCS. Additionally, the study will evaluate if long-term treatment with efgartigimod PH20 SC can prevent relapse.

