2.2 PHASES, PERIODS AND TIME POINTS

2.2.1 *Analysis phases, periods and subperiods*

All assessments and events will be allocated to analysis phases, periods and subperiods as defined in below table.

Table 2: Analysis phase, period and subperiod definition

Phase	Period/Subperiod	Start	End
For participants who don't receive the first IMP administration at the ARGX-113-2010 baseline visit^a, the first phase will be the observation phase.			
For participants who receive the first IMP administration at the ARGX-113-2010 baseline visit^a, the first phase will be the treatment phase.			
Observation		Date of baseline visit in ARGX-113-2010, with 00:00 added as time part	
For participants with a subsequent treatment period:
 
First IMP administration date/time – 1 minute.
 
For other participants:
 
Date of week 48 or EDV visit^c, with 23:59 added as time part.
 
For participants who don't have a week 48 or EDV visit: date of last contact, with 23:59 added as time part.

	Statistical Analysis Plan	
ARGX-113-2010	Final analysis	Final 1.0 of 29APR2025

Phase	Period/Subperiod	Start	End
Treatment	Treatment period 1/ On IMP treatment	
For participants with first IMP administration at the baseline visit:
 
Date of baseline visit in ARGX-113-2010, with 00:00 added as time part.
 
For participants with a previous observation phase and who initiate treatment:
 
First IMP administration date/time
	
For participants with a subsequent Off IMP subperiod:
 
Last IMP administration date/time in treatment period 1.
 
For other participants:
 
Date of week 48 or EDV visit^c, with 23:59 added as time part.
 
For participants who don't have a week 48 or EDV visit: date of last contact, with 23:59 added as time part.

	Treatment period 1/ Off IMP treatment	Last IMP administration date/time in treatment period 1 + 1 minute	
For participants with a subsequent treatment period:
 
First IMP administration date/time in next treatment period – 1 minute.
 
For other participants:
 
Date of week 48 or EDV visit^c, with 23:59 added as time part.
 
For participants who don't have a week 48 or EDV visit: date of last contact, with 23:59 added as time part.

Treatment period 2 is applicable for participants who re-initiate IMP administration after a previous Off IMP subperiod^b.			

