Else, the participant will be considered a non-responder for CROff without IMP. Participants who enter the ARGX-113-2010 study under protocol version 3 (26 April 2024) or 4 (02 May 2024) will be considered non-evaluable for this endpoint. Furthermore, participants who were randomized to the placebo arm in the ARGX-113-2009 study and who enter the ARGX-113-2010 study in the observation phase, will be considered non-evaluable for this endpoint in the observation phase.

- 6) Participants achieving CR or PR while off both OCS and efgartigimod PH20 SC for ≥ 8 weeks (CR/PROff without IMP). A participant will be considered a

	Statistical Analysis Plan	
ARGX-113-2010	Final analysis	Final 1.0 of 29APR2025

responder for CR/PROff without IMP if the following criteria are met simultaneously for ≥ 8 weeks (56 days):

- The participant's reported disease status is CR or PR (continuously or alternately)
- The participant is off OCS therapy
- The participant is off IMP
- The participant does not receive any rescue therapy (as indicated by the investigator on the eCRF)

Else, the participant will be considered a non-responder for CR/PROff without IMP. A participant will be considered non-evaluable for this endpoint using the same rules as for CROff without IMP.

- 7) Duration of sustained remission will be calculated for participants achieving CR while off both OCS and efgartigimod PH20 SC for ≥ 8 weeks (i.e., responders for CROff without IMP) within a treatment period.
 - Start date of sustained remission is 1 week (7 days) after the last IMP administration in the treatment period
 - End date of sustained remission is:
 - the start date of first relapse after achieving CROff without IMP
 - the start date of a (next) treatment period
 - the start date of OCS therapy after achieving CROff without IMP
 - the start date of a rescue therapy after achieving CROff without IMP
 whichever comes first. If none of the above occurs, the participant will be censored at the end date of the study (end date of last phase).
 - Duration of sustained remission (in days) = end date - start date + 1
- 8) Relapse will be evaluated for participants having or achieving CDA, CR or PR during the treatment period (or observation phase). The evaluation period for relapse is till the end of the treatment period (or observation phase) in case a (next) treatment period starts, or else till the end of the study. Only the first relapse in a treatment period (or observation phase) will be considered.

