- 9) Time to relapse:
 - Start date is the first day with status CDA, CR or PR in the treatment period (or observation phase)
 - End date is:
 - the start date of first relapse after having or achieving CDA, CR or PR
 - the end date of the study (end date of last phase), if no relapse
 - Time to relapse (in days) = end date - start date + 1
- 10) For participants with relapse, severity of (first) relapse will be calculated as the BPDAl total score at the onset of relapse (use the first available nonmissing BPDAl total score in the interval of relapse) minus the BPDAl total score at the preceding visit (use the most recent preceding visit for which a nonmissing BPDAl total score is available). Severity of relapse will be categorized as <0 , $0- <10$, $10- <20$, $20- <30$, or >30 .

	Statistical Analysis Plan	
ARGX-113-2010	Final analysis	Final 1.0 of 29APR2025

The following endpoints will be derived **overall**:

- 11) Changes and percent changes from study baseline will be calculated for BPDAI activity and total score.
- 12) Changes from study baseline will be calculated for itch NRS 24-hour average and worst scores.
- 13) C-GTI: Composite Glucocorticoid Toxicity Index comprises the Aggregate Improvement Score (AIS) and the Cumulative Worsening Score (CWS). Details of AIS and CWS derivations are specified in appendix 9.1.
- 14) A total ABQOL score is calculated as the sum of all 17 items score 0 to 3 with higher score indicating worse condition. Missing items are imputed with the average score of the present items if at least half (9) of the items are present. The total score is rounded to the highest integer.
- 15) Changes from study baseline will be calculated for EQ-5D-5L VAS score, DLQI score and total ABQOL score.

4.1.3 *Presentation of results*

Efficacy results will be presented for the ROL analysis set, unless mentioned otherwise. For tables by analysis visit, only the study baseline and last assessment analysis visits will be shown. Other analysis visits will be included in listings.

A frequency tabulation will be created for the number and percentage of participants who achieved CROff at least once during the study (i.e., in any treatment period). The table will also present the number of participants who are evaluable for the endpoint at least once during the study. This number will serve as denominator for the percentage calculation. This table will be based on the SAF analysis set.

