Similar frequency tabulations will be created for the number and percentage of participants who achieved:

- CR/PROff
- CRmin
- Treatment failure

Similar frequency tabulations, based on the ROL analysis set, will be created for:

- CROff without IMP
- CR/PROff without IMP
- Relapse

Duration of sustained remission and time to relapse will be descriptively presented with median times, quantiles and number and percentage of censored observations and observations with event. Only the participant's first evaluation during the study will be included as observation.

Duration of sustained remission will be presented for the SAF analysis set.

A frequency tabulation will be created for categorized severity of relapse, for the participant's first relapse during the study.

	Statistical Analysis Plan	
ARGX-113-2010	Final analysis	Final 1.0 of 29APR2025

Descriptive statistics will present the actual values, changes and percent changes from study baseline of the BPDAl activity and total scores per analysis visit (baseline and last assessment).

Frequency tabulations will be provided for the outcome of IGA-BP per analysis visit (baseline and last assessment). Additionally, cumulative percentages (starting with the best outcome result) will be calculated.

Descriptive statistics will present the actual values and changes from study baseline of the itch NRS 24-hour average and worst scores per analysis visit (baseline and last assessment).

Descriptive statistics will be provided for the C-GTI scores AIS and CWS at the last assessment.

Frequency tabulations will be provided for the outcomes of the ABQOL (17 items), EQ-5D-5L (5 dimensions) and DLQI (10 items), similar to the frequency tabulations of the IGA-BP outcomes. Descriptive statistics on absolute values and changes from study baseline for EQ-5D-5L VAS score, DLQI score and Total ABQOL score will be calculated per analysis visit (baseline and last assessment), similar to the descriptive statistics of the itch NRS scores.

Listings will be created for:

- Disease status, including the derived response variables (CROff, CR/PROff, CRmin, etc.)
- Duration of sustained remission and time to relapse, including the reason for censoring (if applicable) and the severity of relapse
- Lesion assessments
- BPDAl assessments
- IGA-BP assessments
- Itch NRS assessment
- Calculated C-GTI scores and complementary GTI specific list (GTI-SL)
- ABQOL, EQ-5D-5L and DLQI data

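### The relapse tables pool relapses that start on weekly efgartigimod with relapses that start off it, so no planned table gives a relapse rate on maintenance treatment

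*SAP*

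**What the plan says.** SAP section 4.1.2 derives relapse (item 8), time to relapse (item 9) and severity of first relapse (item 10) for each treatment period and for the observation phase. Under item 8 the evaluation window closes at the end of that period or phase "in case a (next) treatment period starts, or else till the end of the study".

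SAP Table 2 (section 2.2.1) places off-drug time inside the treatment period. The Off IMP subperiod of treatment period 1 opens at "Last IMP administration date/time in treatment period 1 + 1 minute". A follow-up phase then runs to last contact. For a participant without relapse, item 9 sets the end date at "the end date of the study (end date of last phase), if no relapse". The Protocol Synopsis states: "A treatment-free period of 8 weeks follows the EoTP visit at week 48".

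SAP section 4.1.3 and the table list plan one proportion (14.2.1.7), one Kaplan-Meier table (14.2.1.8) and one severity table (14.2.1.9). All three use the rollover set under a single total label. For the Kaplan-Meier table, "Only the participant's first evaluation during the study will be included as observation".

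On purpose, the protocol Introduction says "the study will evaluate if long-term treatment with efgartigimod PH20 SC can prevent relapse". The amendment summary gives, as part of the rationale for removing the mandatory stop, the wish to "allow evaluation of whether maintenance therapy with efgartigimod PH20 SC can prevent relapse".

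**The concern.** Relapse during weekly dosing and relapse after dosing has ended answer different questions. The first describes how well maintenance holds the disease. The second describes how durable remission is once the drug is withdrawn. Amendment 2 kept participants on drug partly so that the first could be looked at, but the planned tables merge the two.

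A reader who wants the relapse rate on maintenance will find only the pooled figure and may take it for that rate. The SAP separates exposure elsewhere: concomitant therapies are tabulated by subperiod, treatment-emergent adverse events depend on time since the last dose, and two remission endpoints are defined without IMP. Relapse has no such split.

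**Working it through.** **Step 1: what falls inside the window.** No rule in items 8 to 10 stops the clock at the last dose. Setting those items against SAP Table 2 and the protocol gives:

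| Where the first relapse starts | On efgartigimod? | Counted? |
|---|---|---|
| Observation phase | No | Yes (items 8 to 10 cover this phase) |
| On IMP subperiod | Yes | Yes |
| Off IMP subperiod, after a stop under the pre-amendment-2 rule or a discontinuation | No | Yes (part of the treatment period) |
| Follow-up phase after week 48 or early discontinuation | No | Yes (runs to end of last phase) |

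The protocol schedule has disease assessments at both follow-up visits and at the early discontinuation visit, so off-drug relapses will be recorded.

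**Step 2: share of the window off drug.** Inputs from the documents are 48 weeks of treatment and 8 weeks of follow-up. The clock is taken to start at week 0.
- Relapse-free week-48 completer: 8/56 = 14.3%. Counting the first 7 days after the last dose as on drug, as item 7 does, gives 7/56 = 12.5%.
- Participant who stopped at week s and never restarted: (56 − s)/56. For assumed s = 12, 16 and 24 this is 79%, 71% and 57%.

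**Step 3: effect on the reported proportion.** The documents give no relapse rate, event count or sample size, so there is no stated figure to reproduce. Everything in this step is assumed. Let p be the 48-week on-drug risk, L = −ln(1 − p)/48 the weekly on-drug hazard, and HR the off/on hazard ratio.
- Completer: pooled = 1 − exp[−L(48 + 8·HR)].
- Stopper at week s: 1 − exp[−L(s + HR(56 − s))].

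With p = 0.20, L = 0.2231/48 = 0.00465 per week:

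| HR | Pooled, no stoppers | Share of relapses off drug | Pooled, 20% stopping at week 16 |
|---|---|---|---|
| 1 | 1 − exp(−56L) = 22.9% | 13% | 22.9% |
| 3 | 1 − exp(−72L) = 28.4% | 30% | 32.1% |
| 5 | 1 − exp(−88L) = 33.6% | 40% | 39.5% |

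At HR = 1 the rise from 20% to 22.9% reflects only the longer window.

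**Step 4: the reverse reading.** With no stoppers, p = 1 − (1 − pooled)^(48/(48 + 8·HR)). A reported 30% then fits an on-drug risk of 26.3% at HR 1 or 17.7% at HR 5. With 40% stopping at week 16 and HR 5, solving numerically gives 12.0%. The pooled figure does not identify the on-drug risk.

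**Step 5: items 8 and 9 side by side.** Item 8 ends evaluation when a next treatment period starts. Item 9 ends a record without relapse at study end. Take a participant who is in CDA, CR or PR in the observation phase and starts efgartigimod without relapsing. Only the first evaluation enters the Kaplan-Meier table. Read literally, that observation-phase record is censored at study end and carries on-drug time that item 8 excludes.

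**The case against.** The strongest reply is that the tables match the endpoints as written. The protocol lists the proportion who relapse and time to relapse under long-term efficacy and durability, without limiting them to on-drug time. Section 4.2 also asks whether remission lasts after stopping. A whole-study summary is defensible, and the SAP never labels it a maintenance rate. This stands, and it is why the pooled tables should be kept. It does not supply the on-drug rate that the stated aim calls for.

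Four stronger readings are tempting, and the documents do not support them.
- *Pooling is what prevents the trial from showing that treatment prevents relapse.* The study is single-arm, has no hypothesis tests or estimands, and stops and restarts were not randomised. No tabulation could show prevention.
- *The pooled figure is several times the on-drug rate.* For example, 10% on drug and 30% of the rest in 8 drug-free weeks give 1 − 0.90 × 0.70 = 37%, or 3.7 times. That needs an off/on hazard ratio of (−ln 0.70/8)/(−ln 0.90/48) = 20.3, for which the documents give no basis.
- *Observation-phase entrants contribute only untreated time.* Item 9 can add on-drug time, and some participants not on efgartigimod may be on rescue therapy.
- *Relapse after stopping is hidden.* Table 14.2.1.6 captures part of it, for responders off both OCS and efgartigimod. The listings of disease status, time to relapse and IMP dates hold the rest.

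A fair objection to the remedy is that censoring at the last dose is informative. Participants who stopped before amendment 2 did so because they were in CR or PR, while others stop for treatment failure. The 7-day cut is also a choice: for safety the SAP attributes events up to 60 days after dosing to treatment, longer than the nominal 56-day follow-up. Both points stand as caveats.

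**Conclusion.** The point holds for the planned derivations and tables. The reading of items 8 to 10 and SAP Table 2 is firm: first relapses on and off efgartigimod are pooled, and no planned summary gives an on-treatment relapse rate. The off-drug share of the window (14.3% for a relapse-free completer followed from week 0) comes from the documents' own durations. The size of the distortion does not: 20% becoming 22.9% to 33.6% rests on assumed constant hazards, an assumed on-drug risk and no stoppers. The proportion is raised for certain only among week-48 completers. In the mixed population the direction depends on who stopped. The data are sound and the gap is in presentation, for a secondary endpoint in a descriptive study. The change should be made, but it will not turn the study into a test of prevention.

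**What to change.** 1. Flag each first relapse by phase or subperiod at onset (observation, On IMP, Off IMP, follow-up), and show Tables 14.2.1.7 and 14.2.1.9 by that flag as well as in total.
2. Add a supplementary on-treatment version of Table 14.2.1.8 in the safety set, for the first treatment period. Start at the first day of CDA, CR or PR in the On IMP subperiod. Censor participants without relapse by then at 7 days after the last IMP dose of that period, the convention item 7 already uses. Keep the pooled table. Footnote that a relapse within those 7 days can carry an Off IMP or follow-up flag in step 1 yet count as on-treatment here.
3. Reconcile items 8 and 9, so that a record without relapse ends where its evaluation window ends.
4. State beside the new table that censoring at the last dose is informative and that the estimate is descriptive, not evidence of prevention.

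Cost: SAP wording, one derived flag, one extra table and no new data, since relapse and IMP dates are already listed. The price is smaller counts per stratum and the censoring caveat.

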3. OBJECTIVES, ENDPOINTS, AND ESTIMANDS

Table 4: Study ARGX-113-2010 Objectives and Endpoints

Objectives	Endpoints
Primary	
To assess the long-term safety and tolerability of treatment with efgartigimod PH20 SC in participants with BP	
 • Incidence and severity of treatment-emergent AEs, SAEs, and AESIs • Rate of treatment discontinuation because of safety concerns
Secondary	
To assess the long-term efficacy and durability of response with efgartigimod PH20 SC treatment in participants with BP	
 • Proportions of participants achieving^a: 
 – CR while off OCS for ≥ 8 weeks – CR or PR while off OCS for ≥ 8 weeks – CR while on minimal OCS therapy for ≥ 8 weeks. (Minimal OCS therapy is defined as ≤ 0.10 mg/kg/day of prednisone [or an equivalent dose of another OCS]) – CR while off both OCS and efgartigimod PH20 SC for ≥ 8 weeks^b – CR or PR while off both OCS and efgartigimod PH20 SC for ≥ 8 weeks^b • Duration of sustained remission • Proportion of participants who relapse • Time to relapse • Incidence and severity of relapse • BPDAI activity scores, IGA-BP scores, and itch NRS over time • Rate of treatment failure
Additional secondary	
To evaluate the impact of efgartigimod PH20 SC treatment in reducing long-term glucocorticoid-associated toxicity in participants with BP	GTI-related scores, including the GTI-AIS, GTI-CWS, and GTI-SL over time
To evaluate the impact of efgartigimod PH20 SC treatment on QoL in participants with BP	EQ-5D-5L, DLQI, and ABQoL scores over time
To evaluate the PD and immunogenicity of efgartigimod PH20 SC in participants with BP	
 • Percent change from baseline over time for anti-BP180 and anti-BP230 antibody levels • Incidence and prevalence of ADA against efgartigimod (serum levels)

Objectives	Endpoints
Exploratory	
████████████████████ ████████████████████	██ ████████

^a These endpoint criteria can only be met when participants are off rescue therapy.

^b The endpoint applies only to participants who have stopped receiving efgartigimod PH20 SC before protocol amendment 2 is effective.

No estimands have been defined for this OLE study.

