1.1 STUDY OBJECTIVES AND ENDPOINTS

Table 1: Objectives and endpoints

Objectives	Endpoints
Primary	
To assess the long-term safety and tolerability of treatment with efgartigimod PH20 SC in participants with BP	
 • Incidence and severity of treatment-emergent AEs, SAEs, and AESIs • Rate of treatment discontinuation because of safety concerns
Secondary	
To assess the long-term efficacy and durability of response with efgartigimod PH20 SC treatment in participants with BP	
 • Proportions of participants achieving^a: 
 ○ CR while off OCS for ≥ 8 weeks ○ CR or PR while off OCS for ≥ 8 weeks ○ CR while on minimal OCS therapy for ≥ 8 weeks. (Minimal OCS therapy is defined as ≤ 0.10 mg/kg/day of prednisone [or an equivalent dose of another OCS]) ○ CR while off both OCS and efgartigimod PH20 SC for ≥ 8 weeks^b ○ CR or PR while off both OCS and efgartigimod PH20 SC for ≥ 8 weeks^b • Duration of sustained remission • Proportion of participants who relapse • Time to relapse • Incidence and severity of relapse • BPDAI activity scores, IGA-BP scores, and itch NRS over time • Rate of treatment failure

	Statistical Analysis Plan	
ARGX-113-2010	Final analysis	Final 1.0 of 29APR2025

Additional secondary	
To evaluate the impact of efgartigimod PH20 SC treatment in reducing long-term glucocorticoid-associated toxicity in participants with BP	
 GTI-related scores, including the GTI-AIS, GTI-CWS, and GTI-SL over time
To evaluate the impact of efgartigimod PH20 SC treatment on QoL in participants with BP	
 EQ-5D-5L, DLQI, and ABQOL scores over time
To evaluate the PD and immunogenicity of efgartigimod PH20 SC in participants with BP	
 Percent change from baseline over time for anti-BP180 and anti-BP230 antibody levels Incidence and prevalence of ADA against efgartigimod (serum levels)
Exploratory	
[REDACTED]	
 [REDACTED]

- ^a These endpoint criteria can only be met when participants are off rescue therapy.
- ^b The endpoint applies only to participants who have stopped receiving efgartigimod PH20 SC before protocol amendment 2 is effective.

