14.2 EFFICACY DATA

EFFICACY (14.2.1.X)

14.2.1.1	CRoff: Proportion of Participants Who Achieved CRoff	SAF	EFT07b
14.2.1.2	CR/PROff: Proportion of Participants Who Achieved PR/CRoff	SAF	EFT07b
14.2.1.3	CRmin: Proportion of Participants Who Achieved CRmin	SAF	EFT07b
14.2.1.4	CRoff Without IMP: Proportion of Participants Who Achieved CRoff Without IMP	ROL	EFT07b
14.2.1.5	CR/PROff Without IMP: Proportion of Participants Who Achieved CR/PROff Without IMP	ROL	EFT07b
14.2.1.6	Sustained Remission: Kaplan-Meier Estimates of Duration of Sustained Remission	SAF	EFT09a
14.2.1.7	Relapse: Proportion of Participants with Relapse	ROL	EFT07b
14.2.1.8	Relapse: Kaplan-Meier Estimates of Time to Relapse	ROL	EFT09a
14.2.1.9	Relapse: Frequency Tabulation of Severity of Relapse	ROL	EFT07a
14.2.1.10	BPDAI: Descriptive Statistics of Actual Values, Changes From Baseline, and Percent Changes From Baseline in BPDAI Activity Score over Time	ROL	PDT01
14.2.1.11	BPDAI: Descriptive Statistics of Actual Values, Changes From Baseline, and Percent Changes From Baseline in BPDAI Total Score over Time	ROL	PDT01
14.2.1.12	IGA-BP: Frequency Tabulation of IGA-BP Score Over Time	ROL	EFT07d
14.2.1.13	Itch NRS: Descriptive Statistics of Actual Values and Changes From Baseline in Itch NRS 24-hour Average Score over Time	ROL	EFT03a
14.2.1.14	Itch NRS: Descriptive Statistics of Actual Values and Changes From Baseline in Itch NRS 24-hour Worst Score over Time	ROL	EFT03a
14.2.1.15	Treatment Failure: Proportion of Participants with Treatment Failure	ROL	EFT07b
14.2.1.16	C-GTI: Descriptive Statistics of CWS and AIS over Time	ROL	EFT03a
14.2.1.17	ABQOL: Frequency Tabulation of ABQOL 17 Items Over Time	ROL	EFT07d

	Statistical Analysis Plan	
ARGX-113-2010	Final analysis	Final 1.0 of 29APR2025

14.2.1.18	ABQOL: Descriptive Statistics of Actual Values and Changes From Baseline in ABQOL Total Score over Time	ROL	EFT03a
14.2.1.19	EQ-5D-5L: Frequency Tabulation of EQ-5D-5L 5 Dimensions Over Time	ROL	EFT07d
14.2.1.20	EQ-5D-5L: Descriptive Statistics of Actual Values and Changes From Baseline in EQ-5D-5L VAS Score over Time	ROL	EFT03a
14.2.1.21	DLQI: Frequency Tabulation of DLQI 10 Items Over Time	ROL	EFT07d
14.2.1.22	DLQI: Descriptive Statistics of Actual Values and Changes From Baseline in DLQI Score over Time	ROL	EFT03a
PHARMACODYNAMICS (14.2.3.X)			

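### The separate endpoint on relapse incidence and severity is summarised from first relapses only, so no table gives a relapse count, a relapse rate or the severity of a repeat relapse

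*SAP*

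**What the plan says.** Protocol section 3 (Table 4) and SAP section 1.1 (Table 1) list three relapse endpoints under the secondary efficacy objective. They are "Proportion of participants who relapse", time to relapse, and "Incidence and severity of relapse".

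The SAP handles them as follows.

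- **Derivation, 4.1.2 item 8.** Relapse is evaluated in participants who have or achieve CDA, CR or PR, separately for each treatment period and for the observation phase. "Only the first relapse in a treatment period (or observation phase) will be considered".
- **Derivation, 4.1.2 item 10.** For participants with relapse, "severity of (first) relapse will be calculated as" the BPDAI total score at onset minus the score at the preceding visit.
- **Presentation, 4.1.3.** The relapse tabulation follows the pattern of the CROff table, that is, participants with the outcome at any time in the study. Time to relapse uses only the first evaluation per participant. For severity: "A frequency tabulation will be created for categorized severity of relapse, for the participant's first relapse during the study".
- **Table list, 8.1.** The only relapse tables are 14.2.1.7, titled "Relapse: Proportion of Participants with Relapse", then 14.2.1.8 (Kaplan-Meier time to relapse) and 14.2.1.9 (severity).

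**The concern.** Two endpoints are listed separately, but only one of them has its own analysis of how often relapse occurs. If incidence is read as the share of participants with a relapse, it repeats Table 14.2.1.7. If it is read as a number or rate of relapses, no table reports it.

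The gap matters most under the design in force since amendment 2. Participants stay on efgartigimod to the end of the treatment period. SAP Table 2 (footnote b) opens a new treatment period only after a dosing gap of at least 28 days, so a continuously treated participant has one period and contributes at most one on-treatment relapse.

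Protocol section 2 says the study will look at whether long-term treatment prevents relapse, and the secondary objective includes durability of response. Other tables do not fill the gap: BPDAI, IGA-BP and itch scores are tabulated only at baseline and last assessment. A participant with several mid-study relapses who is clear at the end would appear with one relapse and a good final score.

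**Working it through.** **1. Can relapse recur?** Yes. The protocol's Definitions of Terms require only that CDA has been achieved beforehand. Relapse is not itself among the criteria for permanent IMP discontinuation (7.1.1). Disease status is recorded as dated episodes (SAP 4.1.1), so repeats can be captured.

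**2. How many relapses per participant can each output show?**

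| Output | Maximum per participant |
|---|---|
| Item 8 derivation | one per treatment period or observation phase |
| Table 14.2.1.7 (proportion) | one in the study |
| Table 14.2.1.8 (time to relapse) | one (first evaluation) |
| Table 14.2.1.9 (severity) | one (first in the study) |
| Listings 16.2.6.1 (disease status) and 16.2.6.4 (BPDAI) | all recorded episodes and scores |

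The tables are therefore stricter than the derivation: a participant with two treatment periods also counts once.

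**3. How much could go untabulated?** The plan states no relapse or recurrence rate, so there is no figure to reproduce and what follows is illustration. Let *p* be the assumed share of participants with at least one relapse in 56 weeks, the approximate study duration in protocol 4.1 (56 × 7 / 365.25 = 1.073 years), and let *m* be the mean number of relapses per participant. The untabulated share is 1 − *p*/*m*.

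- *Poisson:* *m* = −ln(1 − *p*). At *p* = 30%, *m* = −ln(0.70) = 0.357, or 35.7 relapses per 100 participants. Thirty are tabulated and 5.7 are not: 5.7/35.7 = 16%. The rate is 0.3567/1.0732 = 33.2 per 100 participant-years.
- *Renewal:* the same hazard, but with no risk for 4 or 8 weeks after each relapse while CDA is regained (simulation, 200,000 participants).
- *Negative binomial, dispersion k = 1 (relapses clustered in some participants):* *m* = ((1 − *p*)^(−k) − 1)/k. At *p* = 30%, *m* = 1/0.70 − 1 = 0.429, and 1 − 0.30/0.429 = 30%.

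| *p* (assumed) | Relapses per 100 (Poisson) | Untabulated: Poisson | Renewal, 4-week gap | Renewal, 8-week gap | Negative binomial, k = 1 |
|---|---|---|---|---|---|
| 10% | 10.5 | 5.1% | 4.4% | 3.8% | 10.0% |
| 30% | 35.7 | 15.9% | 13.7% | 11.9% | 30.0% |
| 50% | 69.3 | 27.9% | 24.5% | 21.3% | 50.0% |

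By construction *p* is the same under every model, so the proportion who relapse does not change. Time to first relapse does not change either.

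**The case against.** **Nothing is lost from the data.** A reader might infer from item 8 that repeat relapses are discarded. They are not: the rule limits a derived variable, and the episodes and BPDAI scores are listed for the whole rollover set. This stands. What remains is that a listed secondary endpoint would have to be counted by hand, by rules chosen after the data are seen.

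**Incidence may mean a percentage of participants.** Neither document defines it for relapse, and SAP 4.3.2.1 defines ADA incidence that way. The reading is permissible. It makes two separately listed endpoints the same, however, and for adverse events the SAP reports participants, events and rates per 100 participant-years (5.1.3). Both usages exist, so the SAP should say which applies.

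**A first relapse already shows that prevention failed.** True, and it is counted. A reader might also infer that the existing relapse results are biased in favour of the drug. The documents do not support that: the proportion and the time to first relapse are correct as derived. Only a total or a rate would be understated, and the SAP does not claim to give one.

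**Later relapses are harder to interpret and to count.** OCS may be adjusted after disease activity (protocol 6.9.1), so a later relapse reflects the drug together with changed OCS. Participants who do not regain CDA despite escalated OCS are treatment failures with their own table (14.2.1.15). After week 8, scheduled visits are 4 or 8 weeks apart, which blurs the separation of episodes. These are reasons for clear rules and cautious reading, not for leaving out the count.

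**The study is descriptive.** No hypothesis test or decision rule depends on the missing count. That limits the weight of the point, but the addition asked for is also descriptive.

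**Conclusion.** The point holds as a reporting gap in a secondary endpoint. Every relapse table is confined to a first relapse, so the incidence and severity endpoint adds only first-relapse severity to what the proportion table already gives. Repeat relapse on continuous treatment, which bears directly on durability, is visible only in listings.

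The size is unknown from the documents. For assumed first-relapse proportions of 10% to 50% over 56 weeks, about 4% to 28% of relapses would be untabulated under Poisson or renewal assumptions, and up to 50% with clustering at dispersion 1. If relapse is rare and does not cluster, the loss is small. The illustration treats every participant as followed and evaluable for the full 56 weeks, whereas risk actually starts at CDA, CR or PR. The change should be made, but no planned conclusion fails without it.

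**What to change.** Keep the first-relapse rules for Tables 14.2.1.7 and 14.2.1.8. For the incidence and severity endpoint, state what incidence means and count each relapse episode that follows a documented return to CDA, CR or PR. Report:

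- the total number of relapses;
- participants with 0, 1, 2 or 3+ relapses;
- the rate per 100 participant-years at risk, where time at risk is time since CDA, CR or PR and not in relapse;
- severity of the worst relapse per participant, beside the first.

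Record the change in SAP section 6, with its timing relative to database lock.

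No new data are needed, since dated disease-status episodes and BPDAI are already collected. The cost is a modest amount of derivation and programming: a rule to separate episodes, a time-at-risk variable, and a pre-relapse BPDAI score for each later episode, plus the added summaries. The sponsor should also expect a less favourable relapse summary if relapses do recur.
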